- Chapter 4: Description of the UCL and INT ethical approvals and inclusion of their approvals in the appendix. Rules for the transfer agreement between CRs and INT for the database transmission and mail address for communication between CRs and INT. Inclusion of the sentences: ” UCL and INT will act as joint Data Controllers for the project, with responsibilities as defined by article 26, GDPR”, “The BENCHISTA project working group includes representation from all PBCRs contributing data to the project, as well as tumour-specific clinical leads from the relevant European clinical trials groups, parent and patient representation and the principal investigators at University College London and INT, Milan.” and “The BENCHISTA data remain the property of the contributing registries, whose consent is required before they can be used for purposes other than those originally envisaged in the BENCHISTA protocols. All members of the Working Group that provide data must be informed of any analysis being carried out.”
- Chapter 6: list of the PMT and IAB members
- Chapter 7: modification of the data providers list
- Use of clinical TNM (cTNM) only for TG Rhabdomyosarcoma tier 2 staging.
- Table 2: Addition of the variables about each exam’s result
- Table 2: Removal of variables about clinical staging documentation and its discrepancy with TG staging
- Table 2: Definition of the residual volume variable for Medulloblastoma as optional
- Table 2: Addition of the modality 3=’Both preoperative and postoperative chemo” and 4=’Chemotherapy only’ in the ‘Chemotherapy type’ variable
- Table 2: Addition of three variables for a possible second previous cancer: ‘second previous cancer’, ‘second previous cancer definition’ and ‘year of diagnosis of the second previous cancer’
- Table 2: Removal of the variable: ‘CT/MRI primary site outcome’
- Change in the meaning of the variable about the examinations/imaging. The meaning has been changed from “examination/imaging used *by the registrar* for obtaining the Toronto stage” to “examination/imaging performed “, even if not used directly by the registrar to construct the Toronto stage. The values and modalities of the variables have not been changed

Amendment N.1 (Protocol version 4.2 to version 4.3) – approved 08 Feb 2022

- UCL and INT will act as joint Data Controllers for the project. Only INT has access to pseudo anonymised personal data and UCL does not. No individual patient-level data will be sent to UCL.

Table 4. Structure of the record.....28

1. Background and aim of the study

Population-based survival studies on childhood cancers (CC) have shown significant geographical disparities and progress during the studied time periods, both within and outside Europe [1,2]. Both time and space outcome differences can be explained by changes in tumour stage at presentation. We know that cancer is diagnosed at a somewhat more advanced stage in the UK compared to several Western European countries and this may be sufficient to explain the small but statistically significant survival differences seen in international comparisons within the same multi-national clinical trial [3]. Additional factors that may explain survival differences between countries are differences in diagnostic accuracy and in treatment [4].

Most population-based cancer registries (PBCRs) hold incomplete data on tumour stage for childhood cancers. This is because staging systems used for adult cancers are not easily applicable to childhood cancer and access to necessary clinical data sources to assign tumour stage is difficult. In 2014, an international working group developed consensus staging guidelines for paediatric cancers, known as the “Toronto” guidelines (TG) [5]. The feasibility of PBCRs applying these guidelines was tested in a pilot study conducted through the European Joint Action on Rare Cancers (JARC)[6,7]. The pilot project was very successful, with a high participation of PBCRs from 14 European countries. It demonstrated the current capabilities and resources required by PBCRs to acquire relevant tumour staging data from clinical registries, treating hospitals or routine health care data sources. For the two solid tumours chosen for the pilot –neuroblastoma and Wilms tumour – tumour stage could be documented for 97% of cases in a recent time period. Several PBCRs were also able to provide data on treatment and relapse.

Application of this standardised way to collect stage and a complete collection of stage at diagnosis on all cases by cancer registries is necessary for comparison and interpretation of any outcome differences in population-based analyses. It should be emphasised that Toronto staging is not used as a clinical instrument for choosing a treatment – this is done using risk stratification criteria defined by the treatment protocol applied to an individual patient and which may vary between countries and treatment centres. The importance of the Toronto staging is as a tool for cancer registries to have comparable stage information at a population-level for each of the commonly recognised childhood cancers.

The broad aims of this project are to improve understanding of the reasons for variation in childhood cancer survival between countries and to highlight areas to be targeted for improvement. Tumour stage is a determinant of the likelihood of cure and the intensity of treatment required by the cancer patient. We aim to stimulate the application of the TG by the greatest number of European PBCRs, for the most common solid paediatric cancers. The collection should be in a routine way, that is stage should be included as a mandatory variable. To do this and for conducting in a sustainable way future outcomes research, closer working relationships between PBCRs, clinical services and tumour-specific clinical study groups should be stimulated.

The specific hypotheses to be tested are:

- 1: Are childhood cancers diagnosed at a more advanced stage in some countries compared to others?
- 2: Do survival rates by tumour stage vary between countries/large geographic regions?

Hypothesis 1 assesses if evidence exists for late diagnosis of cancer in children in some countries. If significant differences are found in the proportion of children diagnosed with more advanced stage tumours, this may be

due to differences in awareness of childhood cancer signs and symptoms (by parents/public and community healthcare workers), or to differences in child health systems for routine surveillance and primary care, or to delays after referral to secondary care. All are potential targets for future interventions.

Hypothesis 2 assesses if evidence exists for variation in survival rates for the same tumour type and stage between countries/regions. If differences are found, this may be due to differences in diagnostic and treatment practices, tumour biology or supportive care. The project will test how well PBCRs can collect data on these items and relapse, so that these further hypotheses can be tested.

These questions will be addressed through the following activities:

1. Participating PBCRs will assign tumour stage at diagnosis at a population level for six specified childhood solid tumours, using the “Toronto” staging guidelines [5,8,9].
2. Participating PBCRs will share a pseudonymised patient-level dataset with the central data analysis team in Milan, including additional variables (feasibility study) where available (non-stage prognosticators, summary of primary treatment, any relapse and cause of death).
3. Comparative analysis of distribution of tumour stage at diagnosis at a population level.
4. Analysis of overall survival by stage for each tumour type, with comparisons between sufficiently large population groups (country-level or European region) for statistically powered analysis of variation and avoidance of reidentification of included cases.
5. Production of practical recommendations on strengthening joint working between PBCRs and clinical/hospital registries so that staging of newly diagnosed childhood cancer patients becomes more efficient and complete. This will allow the analysis of survival by stage to be performed in a sustainable way using routine health care data for prospective clinical observational studies in the future.

The cooperation of PBCRs with clinical/hospital data bases will also assess how easily PBCRs can collect data on first line treatment, tumour biology, non-stage prognosticators (NSP) [9] relapse and cause of death. This feasibility aspect of the project will evaluate how well PBCRs can collect these variables. This information will form the basis for development of future studies that would utilise these data items to explore in more depth the underlying reasons for any variation in survival rates. Collection of these variables will also stimulate collaboration between clinicians in charge of clinical/hospital data bases and registries and their corresponding national/regional population-based cancer registries.

We will also undertake a descriptive comparative analysis of child health practices in the countries of the participating registries. This will cover both routine child health surveillance appointments (frequency and type of practitioner) as well as usual routes to medical attention for symptomatic children. This information will add an extra dimension to understanding variation in ‘routes to diagnosis’ that may explain any observed differences in stage distribution at diagnosis. This information will be compiled from information already in the public domain and discussions with paediatricians and clinicians involved in the project from each participating country.

2. Methodology

2.1 Selection of tumour types

The project will study stage distribution and survival for 6 paediatric solid cancers: **medulloblastoma, osteosarcoma, Ewing sarcoma, rhabdomyosarcoma, neuroblastoma, Wilms tumour.**

These tumours have been selected based on one or more of the following considerations:

1. Generally good prognosis (Wilms tumour, localised neuroblastoma) and curability using 'standard of care' treatment regimens.
2. The important differences in outcomes already demonstrated between some populations for some tumour types.
3. Low or no improvement in survival rates over a long time period.

Together, they represent a considerable percentage (~40%) of all childhood solid tumours. The expected number of cases estimated by country for the three-year inclusion period for this study is shown in Table 1. The numbers of cases are estimated mostly from data held by the EURO CARE-6 project (2005-2013) [10].

2.2 Inclusion criteria

The updated ENCR (European Network of Cancer Registries) recommendations (<https://encr.eu/sites/default/files/pdf/incideng.pdf>) should be followed to record the date of incidence used by the registry to define their cases meeting the inclusion criteria.

- Cases to be included are all children aged <15yrs with the relevant histology codes (detailed in the Appendix that describes the Toronto staging systems for each tumour type). For the three cancer types that are common in adolescents (osteosarcoma, Ewing sarcoma and rhabdomyosarcoma), cases aged 15 -19 (inclusive, i.e., < 20) years of age will be included if data are held by the registry.
- Cases must be diagnosed between 01.01.2014 – 31.12.2017, one year incidence back and forth will be considered in order for a registry to have a minimum of three consecutive years' worth of cases, providing 3 years follow-up is assured.
- All consecutive incident cases must be identified and submitted by each PBCRs.
- Cases should have at least 3 years of follow-up for the definition of the life status, according to PBCR practice.
- After an agreement with the INT team, follow up data could be submitted separately and at a later timepoint during the second year of the project, to allow for maximum follow-up on all patients.

Cases with problems in the definition of stage because of scarcity of information must be included and not eliminated.

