2.8 Statistical considerations

The main endpoints for the statistical analyses, by tumour type, are:

1. Differences in stage distribution between countries/regional groupings.
2. Survival differences between countries/regional groupings, and how much of any difference is explained by variations in stage distribution and/or survival by stage.

The formal statistical power to detect differences in stage distribution and survival rates between countries is necessarily limited by incident numbers of each of the six tumour types per country over the recent time period for which PBCRs are able to provide tumour stage. Therefore, analyses of stage distribution and survival rates for each tumour type per country will be descriptive, with 95% confidence intervals reported.

Approximately 8,000 cases will be included (table 2). As the study is population-based, these are the largest numbers available and are not biased in the ways that might affect institutional or clinical trial series.

Endpoint 1: To formally assess if differences in tumour stage at diagnosis are significant, we will group European countries according to the regional geographies used in EURO CARE 5 to achieve the group sizes necessary. Non-European jurisdictions will be considered individually. For expected case numbers by registry (table 2), we have approximately 60% power to detect a 10% difference in lower stages (localised, loco-regional) versus more advanced stage (metastatic) between two countries or regional groupings where there are 250 cases of each tumour type in each group (medulloblastoma, Wilms tumour). For group sizes with 300 cases (neuroblastoma), the power would be 70%. We will combine the sarcomas, who collectively comprise 29% of the cohort, for assessment of differences in stage distribution at diagnosis, according to the same country groupings.

Endpoint 2: Overall survival for each tumour type will be analysed for all patients and broken down by appropriate tumour stage, using standard Kaplan-Meier methods reported with 95% CIs. Survival differences between countries/regional groupings and how much is explained by variations in stage distribution will be studied by multivariable Cox regression including stage and other relevant prognostic variables (age at diagnosis, sex and/or primary site for at least some diagnostic groups), and confounders including stage migration.

3. Oversight and funding of the project

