Malta	ML_Malta National	2	2	3	1	1	2
Norway	NO_Norway National	24	22	20	17	10	13
Poland	PL_Poland National	117	136	119	86	68	86
Portugal	PT_Central Portugal	9	8	6	4	3	5
	PT_North Portugal	10	23	13	9	10	11
	PT_South Portugal	17	25	18	13	8	15
Slovakia	SK_Slovakia National	20	28	23	22	16	15
Slovenia	SL_Slovenia National	7	5	7	6	4	6
Spain	SP_Balearic Islands	2	4	5	3	3	2
	SP_Basque Country	7	13	6	5	5	5
	SP_Canarie	3	8	5	4	3	6
	SP_Castellon (general)	3	2	1	2	3	3
	SP_Com_Valenciana, Childhood	17	28	13	11	12	13
	SP_Girona	2	4	2	3	2	2
	SP_Granada	3	5	4	3	3	3
	SP_Murcia	6	8	5	5	5	4
	SP_Navarra	3	4	3	2	2	2

	SP_RETI-SEHOP (Ba_Ma), Childhood	34	63	36	15	26	22
	SP_Tarragona	3	6	3	2	3	2
Switzerland	SW_Switzerland National, Childhood	27	34	27	14	13	22
The Netherlands	NL_The Netherlands National	66	74	74	61	44	52
England	UK_England National	157	226	213	156	100	156
Northern Ireland	UK_Northern Ireland National	8	8	7	5	6	8
Scotland	UK_Scotland National	19	23	16	15	17	19
Wales	UK_Wales National	11	13	11	10	6	9
Italy	Campania*	21	37	22	11	11	13
Italy	Pavia*	2	3	2	1	1	1
Canada	Canada*	-	-	-	-	-	-
Romania	Romania*	84	129	66	31	27	25
Australia	Australia*	99	135	105	42	45	69
Japan	Japan*	53	96	33	13	11	37

*Not in EURO CARE 6 **0-17 years old ‘-‘ Number of cases not known
							

Table 4. Structure of the record

Variable	No. of characters	Notes and encoding
Basic variables		
Registry	10	alphabetic
Registry Patient Identification code	10	assigned by the registry, it is a project-specific pseudonymised code
Year of birth	4	yyyy
Age at diagnosis	3	Numeric (in months)
Year of diagnosis	4	yyyy
Sex	1	boy/girl/unknown 1/2/9
Base of diagnosis (as coded in the ENCR protocol)	1	DCO/Clinical/Clinical investigation/Specific tumour markers /Cytology/Histology of a metastasis/Histology of a primary tumour /Unknown 0/1/2/4/5/6/7/9
ICDO-3-Topography	3	Only the numeric part of the ICD-O-3 topography code will be reported (the "C" and "." will not be included)
ICDO-3-Morphology	4	Malignant, only, behaviour=3
First previous cancer	1	Y/N/unknown 1/0/9
First previous cancer definition		International Classification of Childhood Cancers (ICCC) 3rd edition
Year of diagnosis of the first previous cancer	4	yyyy / 9
Second previous cancer	1	Y/N/unknown 1/0/9
Second previous cancer definition		International Classification of Childhood Cancers (ICCC) 3rd edition
Year of diagnosis of the second previous cancer	4	yyyy / 9
Imaging/examination used for staging before any treatment		

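### Registries may contribute different diagnosis years, but section 2.8 does not name year of diagnosis in either between-country comparison; the likely bias is small and cheap to remove

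*Protocol*

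**What the plan says.** Protocol section 2.2 sets the core window: "Cases must be diagnosed between 01.01.2014 – 31.12.2017". It then relaxes it: "one year incidence back and forth will be considered in order for a registry to have a minimum of three consecutive" years of cases, with the condition "providing 3 years follow-up is assured".

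Section 2.8 describes the two comparisons. For the formal Endpoint 1 comparison of stage, "we will group European countries according to the regional geographies used in EURO CARE 5 to achieve the group sizes necessary", while non-European jurisdictions are taken one by one. No covariate is named. Per-country results are descriptive, with 95% confidence intervals. For Endpoint 2 the Cox model is described as "including stage and other relevant prognostic variables (age at diagnosis, sex and/or primary site for at least some diagnostic groups"), followed by confounders, of which stage migration is the only one named.

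Table 4 lists "Year of diagnosis" among the basic variables, without the asterisk that marks optional items. On time itself, section 1 says: "Both time and space outcome differences can be explained by changes in tumour stage at presentation".

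**The concern.** The project asks whether stage at diagnosis, and survival within stage, differ between countries. Section 1 treats time as well as place as a source of outcome differences. The top-up rule in section 2.2 lets calendar period differ by registry, so period can become associated with country or region. If imaging, referral or treatment changed everywhere over these years, a group with more early cases would differ from one with more late cases even if the countries were identical in any given year. Nothing in section 2.8 names a control for this: no year covariate, no stratification by year, no restriction to common years. Hypothesis 1 would then read part of a time trend as late diagnosis in some countries, and Hypothesis 2 could read it as a difference in care or biology.

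**Working it through.** **1. Which years can be compared.** With 2014-2017 alone, the runs of at least three consecutive years are 2014-2016, 2015-2017 and 2014-2017; any two share at least two years. With 2013 and 2018 allowed there are 10 possible runs, and exactly one pair shares no year: 2013-2015 v 2016-2018. This pair fits the purpose of the rule: a registry holding only 2014-2015 adds 2013, and one holding only 2016-2017 adds 2018. Follow-up does not exclude 2018: a case diagnosed on 31.12.2018 reaches three years on 31.12.2021, before the November 2022 deadline in section 2.6.

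**2. The test.** Section 2.8 states about 60% power for a 10-point difference with 250 cases per group, and 70% with 300. The test, level and base rate are not stated. Assume a two-sided 5% z test of two proportions, with d = p2 − p1:

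- SE0 = √[2p̄(1−p̄)/n], SE1 = √{[p1(1−p1)+p2(1−p2)]/n}
- Rejection probability = Φ[(d − 1.96·SE0)/SE1] + Φ[(−d − 1.96·SE0)/SE1]

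With 50% v 60% and n = 250: SE0 = 0.0445, SE1 = 0.0443, power = Φ[(0.10 − 0.0872)/0.0443] = 61.4%. With n = 300 it is 69.3%. The plan's figures are reproduced, so the same test is used below.

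**3. Gap in mean diagnosis year.** Assume equal numbers of cases per year. The means are 2014 for 2013-2015, 2015.5 for 2014-2017 and 2017 for 2016-2018.

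- 30% of one group from 2013-2015, all else core: 0.30 × 1.5 = 0.45 years.
- 30% of both groups shifted, in opposite directions: 2 × 0.45 = 0.9 years.
- One group wholly 2013-2015, the other core: 1.5 years.
- Both wholly shifted, in opposite directions: 3 years.

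**4. Spurious difference and error rate.** The documents give no trend. Assume the metastatic share moves by 0.5 to 2 points per year everywhere, there is no true country difference, the base share is 30%, and n = 250 per group. Spurious difference = gap × trend.

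| Composition | Gap (years) | Spurious difference (points) | Rejection at nominal 5% |
|---|---|---|---|
| 30% of one group shifted | 0.45 | 0.2 to 0.9 | 5.0% to 5.6% |
| 30% of both, opposite directions | 0.9 | 0.45 to 1.8 | 5.1% to 7.2% |
| One group wholly shifted v core | 1.5 | 0.75 to 3 | 5.4% to 11% |
| Both wholly shifted, opposite | 3 | 1.5 to 6 | 6.5% to 30% |

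Example, second row, upper end: d = 0.018, SE0 ≈ SE1 ≈ 0.0413, so Φ(−1.52) + Φ(−2.40) = 0.064 + 0.008 = 7.2%. With a 50% base share the last row becomes 6.3% to 27%.

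**5. Jurisdictions considered individually.** These are not diluted by pooling, but they are smaller. The case-number table lists 99, 135 and 105 cases for Australia and 53, 96 and 33 for Japan (embryonal CNS tumours, neuroblastoma, renal tumours). Replacing 1/n + 1/n by 1/105 + 1/250 in the standard errors, a wholly shifted jurisdiction of 105 cases against a core group of 250 gives 5.2% to 8.3% for 0.75 to 3 points. The documents do not say whether any jurisdiction shifts.

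**6. Restricting to 2014-2017.** This turns 2013-2015 v 2016-2018 into 2014-2015 v 2016-2017. These still share no year, and their means (2014.5 and 2016.5) are 2 years apart.

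**The case against.** Several points on the other side stand.

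- A full covariate list is commonly left to a statistical analysis plan, which is not shown. The Endpoint 2 confounder list is open, so year of diagnosis can enter it. A reader might infer that the protocol has decided against adjusting for year; the text supports only that year is not named. This softens the point for Endpoint 2. It does less for Endpoint 1, where no adjustment of any kind is described.
- A reader might take section 2.2 to let any registry move its window freely. It does not: the extra year is to be considered, and only so that a registry reaches three consecutive years. How many registries use it is not stated.
- A reader might carry away error rates of 11% or 30%. At 250 cases per group, these need at least one group to be wholly shifted (11%) or both, in opposite directions (30%), and an assumed trend of 2 points per year. European countries are pooled into regions for the formal comparison, which makes such compositions unlikely.
- Section 1 names time as a source of difference but gives no rate. Section 2.1 lists low or no improvement in survival among its tumour selection considerations, which points to a small trend for survival, though not for stage. Stage migration is a named confounder and examinations performed are recorded, so part of the imaging mechanism can be examined.

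What remains is that the protocol's own window rule creates the calendar imbalance, and a collected variable that would address it is not named.

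**Conclusion.** The point holds at low severity. Sections 2.2 and 2.8 together allow a common time trend to enter the between-country comparisons as a geographical difference, clearly for Endpoint 1 and, because its confounder list is open, less firmly for Endpoint 2. After regional pooling the effect is probably a fraction of a point to under 2 points in the metastatic share, with a false-positive rate of about 5% to 7% in place of 5%. It is larger only for jurisdictions considered individually or for wholly shifted groups. These sizes rest on an assumed trend of 0.5 to 2 points per year, equal cases per year, a 30% base share, 250 per group and assumed fractions of shifted cases. The survival effect was not quantified. The documents do not show that any planned comparison is materially biased.

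**What to change.** In section 2.8:

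- Name year of diagnosis as a covariate in the Endpoint 2 Cox model.
- Make the Endpoint 1 group comparison year-adjusted, for example a logistic model with group and year, fitted across all registries so that the trend is estimated from overlapping years.
- Report the diagnosis years that each registry contributes.
- Add a sensitivity analysis limited to the calendar years that the compared groups share. Restriction to 2014-2017 alone does not guarantee a common period.

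The cost is a few sentences and one or a few degrees of freedom; no new data or cases are needed. The limit is that groups with no common year rely on a modelled trend and have no shared-year sensitivity analysis, which should be stated wherever such a comparison is reported.
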